## 2. BACKGROUND

Approximately 1,000,000 lung nodule and other abnormal lesions such as GGO (ground glass opacities) are detected in people in the United States each year. Lung nodules are found on 1 in 500 chest x-rays, and 1 in 100 CT scans of the chest. In reported studies, up to 51% of smokers aged 50 years or older have pulmonary nodules/lesions on CT scans.

A solitary pulmonary nodule is defined as a discrete, well-margined, rounded opacity less than or equal to 3 cm in diameter that is completely surrounded by normal lung parenchyma, does not touch the hilum or mediastinum, and is without associated atelectasis or pleural effusion. GGO (Glass Ground Opacity) refers to specific changes in the lung parenchyma on CT that may represent tumor, pre-malignant lesion or other benign lung lesions.

Whether detected serendipitously or during a routine investigation, solitary pulmonary nodules/lesions pose a challenge to both clinicians and subjects[1]. A nodule on a chest radiograph raises several questions: Is the nodule benign or malignant? Should it be investigated or observed? Should it be surgically resected? The clinical context is also important and includes age, history of immunodeficiency (inherent or due to disease, chemoradiation, diabetes), travel history in endemic area for specific pulmonary pathogens (Ohio River valley, San Joaquin Valley, TB endemic areas), current infectious symptoms etc. In different clinical

CONFIDENTIAL

This document is confidential. Do not disclose or use except as authorized.

circumstances the lesions/nodules can represent specific infections, benign growth, cancers or intrinsic pulmonary abnormalities.

Most solitary pulmonary nodules are benign. Seventy five percent of nodules less than 2 cm are benign [2] but they may represent an early stage of lung cancer. Lung cancer survival rates remain dismally low at 16% at 5 years [3,4]. If detected early enough, lung cancer can be treated and survival chances improved [5,6]. Early lung cancer, when the primary tumor is less than 3 cm in diameter (stage 1A or 1B), may lead to 5-year survival rates as high as 70-80%, yet only 15% of lung cancers are diagnosed at this early stage [3]. Likewise, a benign diagnosis can relieve patients from the radiation burden of follow up with CT scans and in some cases can provide a life saving treatment with steroids, antibiotics etc.

Recently, a large prospective randomized trial demonstrated that screening subjects at risk for lung cancer based on age and smoking history with chest computed tomography (CT) reduces the mortality from lung cancer [7,8]. The National Lung Screening Trial (NLST) involving more than 53,000 heavy smokers resulted in 20 percent fewer lung cancer deaths among trial participants who met specific criteria and were screened with low-dose helical CT [9]. As a consequence of this positive study, it is expected that hundreds of thousands of subjects with lung nodules/lesions will come to surgical biopsy. Statistically, the majority of these people will have benign diseases, but definitive diagnosis will be required in those with sufficiently large lesions or in radiographically suspicious lesions. Furthermore, subjects with very small lesions (<<1cm) that are suspicious for cancer will be discovered that are challenging to resection using current surgical techniques. Thus new protocols are required to improve resection accuracy, preserve normal lung and reduce morbidity, mortality and costs to society.

Based on clinical circumstances, lesions discovered on CT screening may be followed up radiographically or subjects may be referred for biopsy, radiological or surgical. The decision tree is based on size, appearance and clinical scenario (true for lesions suspected of either malignant or non-malignant etiologies). The protocol described herein, is designed for and limited to subjects who are referred for surgical biopsies.

Screening with computed tomographic (CT) scans has to some degree changed the technologies available for surgery for both lung cancers and for benign diseases. In the past and for most cases in the US currently (>75%), most lung cancers were relatively large and subjects required open thoracotomy for resection. Now-a-day, many cancers are much smaller and can be accessed through minimally invasive approaches, Video Assisted Thoracic Surgery (VATS) [10]. This is particularly the case in specialized centers such as BWH where most Thoracic Surgeons will attempt VATS resection for the majority of pulmonary nodules for any etiology. The same applies to non-cancerous nodules that need to be biopsied or resected for diagnosis and/or treatment. This surgery is routinely performed through 3 small incisions (1cm or so each) whereby one incision is used for the placement of a rigid video telescope camera and the other incisions are used to grab and mobilize the lung, bring it closer to one incision which will allow palpation of the lung with a finger tip

CONFIDENTIAL

This document is confidential. Do not disclose or use except as authorized.

to identify the nodule/lesion that will then be cut out using a stapling device. We recently reviewed (unpublished results submitted for publication) all subjects aged 21-85 years who had surgical resection for small ( $\leq 2\text{cm}$ ) non-small cell lung cancer at BWH from 2004-2008. Of 347 subjects, 10.1% experienced  $\geq 1$  major complication and 16.1% a hospital stay of  $\geq 1$  week. The complications included: Adult respiratory distress syndrome (1), Aspiration (1), Bronchopleural fistula (1), Cerebro vascular accident (1), Empyema (1), Myocardial infarction (1), Pulmonary edema (1), Pulmonary embolism (1), Ventilator for more than 7 days (1), Wound infection (1), Chylous leak (2), Tracheostomy (2), Acute renal failure (3), Atrial fibrillation (4), Re-operation due to bleeding (4), Re-intubation (5), Pneumonia (7), Air leak for at least 7 days (20). Of interest we also found that for a 30-minute increase in operative time, the odds of  $\geq 1$  major complication are estimated to increase by 103% (OR 2.03; 95% CI: 1.45-2.84), supporting the need to reduce operative time with a strategy such as proposed in this protocol. Though these complications and rates are only representative of one specific subset of our subjects they provide a highly relevant snap shot of rates and types of complications expected in this protocol.

**The crux of the challenge and the reason for this protocol is that at surgery, many of these nodules/lesions are hard to palpate and to precisely define their location for resection.** This is particularly true for smaller nodules or GGOs, precisely the ones that require resection to provide early diagnosis and therapy since at least half may be benign. Thus, using current technologies, which are non-image guided, result in three potential non-ideal outcomes: 1. A more extensive resection of normal lung parenchyma (such as lobectomy or segmentectomy) to make sure that the lesion is included even if it is non-palpable; 2. An enlargement of at least one incision to insert the hand into the chest for better physical definition-resulting in a more painful and complex recovery for the subject with resulting longer recovery, chronic pain and greater cost; 3. Too close a surgical margin to the cancer requiring re-operative surgery of increasing the chance of recurrence.

The concept of intra-operative imaging-guidance is not new and has been used for breast biopsy (needle localized breast biopsy) for many decades and more recently for neurosurgery. There are also a few reports in the literature using similar marking as for breast biopsies for lung lesions (using either a dye or the same coil as breast biopsies). The reports show that this is a safe and effective strategy [11-17]. However, the difference between what was previously reported in a few publications from what we propose herein is that the previous markings have been done at some time pre-operatively in a CT scanner as opposed to on the operating table with fluoro CT capabilities as available in AMIGO. The former approach limits the types of nodules that could be accessed because lack of general anesthesia and potential risk of pneumothorax which are eliminated in our protocol by having lung isolation already in place. Our approach is perform the -CT-guided marking directly in the operating room allowing for both marking and intra-operative tracking as required to ensure complete resection without moving the subject .

The AMIGO suite at BWH is an innovative operating room that allows for concurrent radiological imaging. It has a centralized, fully equipped and credentialed operating room with all the amenities as well as a fluoro-CT, movable MRI, Focused US and a PETCT area. The AMIGO suite is unique NIH funded resource for developing and perfecting novel surgical procedures which require imaging support. The intention is to develop these types of procedures in the AMIGO suite and then to modify them so that the successful procedures may be performed in the operating rooms. Parenthetically, an identical fluoro-CT is also available in one of the BWH operating rooms.

Our goal in this protocol is to enroll subjects who require VATS for specified lung lesions, have the subject be operated in the AMIGO suite where they undergo the following process: intubated with a double lumen tube, positioned in the lateral decubitus position, undergo CT- to confirm the location of the nodule, perform image guided needle biopsies and mark the lesion by placing a needle guided hookwire and/or T-bar. At this point, VAT surgery will be performed to resect the lung lesion utilizing the marking, which will remove the hookwire and/or T-bar with the specimen. The specimen will then be removed in an Endo-bag and submitted for a quick CT picture (away from the subject) and sent for pathological analysis. Only the underlined elements are experimental, the operation itself and indications are standard of care. The intentions are to define the methodology, risks, exposure etc. and then work in follow-up trials to potentially improve upon the marking device and the procedure to get them to the point where this approach is available for any subject undergoing lung resection. We believe that this is a game changing approach that is long overdue for thoracic surgery.

The second aim of this proposal takes advantage of the design of the protocol. In addition to placing an image guided marker, we propose to also obtain FNA from the lesion to be used for both cytological and molecular analysis. The results supporting this proposed aim come from our laboratory where through NCI funded projects we developed molecular tests based on gene expression strategies to distinguish normal lung from lung cancer [18] and mesothelioma from other cancers. We currently have a separate open clinical trial (with IRB approval) to obtain FNA biopsies under image guidance with ultrasound in subjects with mesothelioma (DFCI IRB protocol number 04-349). To-date about 115 subjects underwent this procedure with no complications [19].

The genetic analysis for this protocol involves taking the specimens obtained during the FNA procedure and using the RNA from these specimens to make cDNA. This cDNA will be used for transcriptional profiling and RNA sequencing. This will be done both in the tumor specimen as well as the adjacent normal specimen.

### **3. Participant SELECTION**

#### **Subject Selection:**

This study will be initially limited to subjects with lung nodules or lesions 3cm or smaller in the outer half portion of the lung/lobe and who are candidate for VATS at

CONFIDENTIAL

This document is confidential. Do not disclose or use except as authorized.

DFCI or BWH and consent for the procedure. The subjects will be formally consented at BWH only. The subjects may initially be told about the research procedure during a visit at DFCI with their thoracic surgeon, but if they choose to participate in the trial they will be consented at BWH. The CT will be reviewed by the study radiologist and thoracic surgeon prior to enrollment. At least 25 subjects scheduled for lung resection surgery will be enrolled to the study. The goal is 25 subjects who are enrolled into the trial.. All subjects will be chosen from the outpatient clinic of Thoracic Surgery, BWH.

### **3.1 Eligibility Criteria**

Participants must meet the following criteria on screening examination to be eligible to participate in the study:

- **Subjects Procedures** – subjects who are candidate for VATS and were consented for the procedure will be eligible for enrolled to the study.
- **Measurable Nodule** – lesions that are nodules/GGO or other abnormal opacity that can be accurately measured in at least one dimension with longest diameter <= 30 mm using conventional techniques.
- **Nodule Location** - lesions that are located in the outer half portion of the lung/lobe.
- **Enrolment Site** – Subjects who are seen at BWH and or DFCI Thoracic Surgery outpatient clinics. However, the subjects will formally consented at BWH only.
- **Age** – Enrollment at Partners will be limited to adults, 18 years and older.
- **Number of subjects** = 25 subjects will be enrolled to this stage of the study. Adult subjects, non-pregnant, non breast feeding to avoid radiation exposure. Urine and/or blood pregnancy test will be obtained based on clinical indications.

## **4. SUBJECT ENROLLMENT**

We will use our clinical research standard operational procedures to recruit subjects ensuring that the confidentiality and privacy of potential subjects are protected. Potential subjects will be identified by their thoracic surgeon attending and other surgeon investigators during their visit to the outpatient clinic. These thoracic attendings have firsthand knowledge of the subject's medical history. The surgeon will evaluate and initially discuss the research with the subject. If the subject agrees to participate in the research, the surgeon will obtain verbal consent from him/her to be contacted by the research staff. However, informed consent will be obtained by a licensed physician investigator.

Consent will be obtained by a licensed physician investigator at least a day prior to the start of the study procedures.

In addition:

- The CRA will ensure that subject identification is on all pages of the CF.
- There is documentation that the subject is given a copy of the consent form.
- Clinic research note documenting informed consent process.

CONFIDENTIAL

This document is confidential. Do not disclose or use except as authorized.

- The subject and study representative signed and dated the consent form for him/herself.
- The subject initialed and dated all appropriate pages on the informed consent form.
- Note to file made for any informed consent deviations.
- The CRAs will ensure that a valid (current version date) copy of the consent form was used.
- Eligible participants will be registered in an enrollment log by the CRAs.
- Following registration, participants should begin protocol as soon as their procedure is scheduled. If a participant does not receive protocol treatment/procedure, the participant's protocol status will be changed (off-protocol)

CONFIDENTIAL

This document is confidential. Do not disclose or use except as authorized.

## 5. STUDY PROCEDURE

**For Aim 1:** To determine the feasibility of image guided VATS resection using AMIGO for lung lesions/nodules in subjects scheduled for lung resection surgery.

In practice, the subject will be placed under general anesthesia in an operating room with CT capabilities. The Advanced Multimodality Image Guided Operating (AMIGO) Suite is an innovative surgical and interventional environment that is the clinical translational test bed of the National Center for Image-Guided Therapy (NCIGT) at the Brigham and Women's Hospital (BWH) and Harvard Medical School. In AMIGO, real-time anatomical imaging modalities like x-ray and ultrasound are combined with cross sectional digital imaging systems like CT, MRI, and PET. There are two such rooms (with fluoro-CT) at the BWH currently, one in an AMIGO suite and the other being the hybrid operating room #1.

After the subject is asleep and appropriately positioned in lateral decubitus with a double lumen endotracheal tube in place, a brief image of the region of interest in the chest and or lung will be generated with the fluoro-CT and be fused with the preoperative CT (in this way minimizing exposure to radiation). Based on each subject's weight they will either receive their initial scan by Dyna-CT or by CT both of which are available in the AMIGO operating room suite. A needle will then be guided into the lesion under fluoroscopy, biopsies will be obtained and a hookwire and/or T-bar device will be placed through the needle, several needle passes may be required which is standard for image guided biopsies and localizations. The hookwire and/or T-bar are metallic objects that can be tracked with imaging and be used to precisely locate the lesion using imaging. Since it is better visualized on imaging than the original lesion, it is easier to track even when the lung is collapsed as it is in preparation for surgery. For the initial work in this protocol we proposed to use a hookwire and/or T-bar [Picture 1, 2, 3 and 4].

[figure not shown]
Each device is connected by a suture to the outside of the chest wall to allow constant guidance. Also, by visualizing the tract of the suture one can see where it enters the lung. Depending on the extent and location of the lesion one or two such devices may be placed (if needed to encompass the borders of the lesion). Once the device is placed, standard video assisted lung surgery will commence using 3-4 incisions, rigid video telescope camera and fluoroscopy if needed will guide the localization of the nodule. The lung around the nodule will then be grasped and resected with the hookwire and/or T-bar within it. The specimen will be then removed, investigated with imaging (away from the subject to avoid unnecessary radiation) to confirm that the original lung nodule/lesion is within and then taken to pathology to confirm that an abnormal nodule was resected and that the margins are appropriate, following our standard of care. The operation will then proceed and be concluded per standard of care.

**Picture 1, 2:** Metallic Hookwire that can be tracked with imaging. In picture 1:

CONFIDENTIAL

[figure not shown]
This document is confidential. Do not disclose or use except as authorized.

Human lung specimen (staples in the perimeter of the biopsy)- the tip of the Kopan's wire is market with red arrow

Picture 1

[figure not shown]
In picture 2: Wire in a breast tissue.

Resected Breast specimen radiograph with  
Kopan wire in it

Picture 2

In picture 3 and 4: Metallic T-bar that can be tracked with imaging.

**For Aim 2:** to determine whether molecular analysis of the nodule in conjunction with cytology using Fine Needle Aspirations FNAs can predict diagnosis and outcome. Aim 2 is based on preliminary work from our group showing that molecular analysis of FNA from thoracic lesions can provide accurate diagnosis. Since the subject will be in a position under general anesthesia to undergo needle placement of the hookwires and/or T-bar, we request permission for two more needle passes prior to it to obtain material for cytology and molecular testing to determine the diagnostic accuracy of combining the two. This is based on an approved protocol (DFCI 04-349 FINE NEEDLE BIOPSIES IN MPM) for which over 100 subject have been enrolled with no complications and diagnostic accuracy for mesothelioma of 93%. We anticipate that in this setting there should not be added risk to the subject .

Study endpoint: morbidity rate, 25subject .

### 5.1 Device

Metal wire, FDA approved like: Kopans Lesion Localization Hookwire.  
<http://fdazilla.com/fda/devices/search?q=hookwire>

Metal T-bar, FDA approved like: Gastrointestinal Anchor Set with SaF-T-Pexy T-Fasteners by Kimberly-Clark Franklin, MA 02038 [name]

### 5.2 Duration of Follow Up

Participants will be followed after removal from study for 12 months.

## 6. BIOSTATISTICIAN ANALYSIS

Percutaneous image-guided VATS resection of lung lesions will be considered to have acceptable morbidity if major complications were observed among 3 or fewer of the 25 subject total. The decision rule achieves 76% power to detect a 10% morbidity rate and accept the alternative hypothesis of non-inferiority of the protocol procedure. In contrast, the decision rule is associated with only 10% probability if the morbidity rate were truly 25% and thus unacceptably higher than the expected rate of 5-20%.

In order to protect the privacy and confidentiality of subjects, data retained in our research laboratories or sent to collaborators will be labeled with an alphanumeric code rather than with the subject's name, initials, medical record number, date of birth, or Social Security number.

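### Does the decision rule need a stated replacement rule, given that the 25 subjects are counted as enrolled rather than treated?

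*Combined protocol and SAP*

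**What the plan says.** Section 6 of the combined protocol and SAP calls morbidity acceptable "if major complications were observed among 3 or fewer of the 25 subject total". It gives this rule 76% power at a 10% morbidity rate and a 10% probability of acceptance at 25%.

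The number 25 is stated by enrolment in three places. Under Subject Selection in Section 3: "At least 25 subjects scheduled for lung resection surgery will be enrolled to the study" and "The goal is 25 subjects who are enrolled into the trial". In Section 3.1: "25 subjects will be enrolled to this stage of the study".

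Section 4 separates enrolment from treatment. "Consent will be obtained by a licensed physician investigator at least a day prior to the start of the study procedures", and eligible subjects go into an enrolment log before the procedure. It also provides for a registered subject who is never treated: "If a participant does not receive protocol treatment/procedure", the status becomes off-protocol. Nothing more is said about that subject.

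Two other places bear on the meaning of the 25. The study endpoint line at the end of Section 5 names the morbidity rate and 25 subjects together. The sentence in Section 6 that holds the rule has the image-guided resection itself as its subject.

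**The concern.** The 10% at a true 25% rate is the only limit the plan states on wrongly accepting the procedure. It is a binomial figure for 25 subjects who all carry the procedure's risk. The sample-size statements speak of enrolment, and the plan expects that some enrolled subjects may not be treated. Such a subject says nothing about the morbidity of marker placement. If that subject filled a place among the 25, or was dropped while the limit stayed at 3, the rule would be easier to pass than stated.

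A choice made late could also settle a borderline result. Three events among 22 treated subjects, with three untreated subjects making up the 25, would pass. Three further treated subjects might bring a fourth event.

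**Working it through.** **Inputs.** From Section 6: limit 3, n = 25, acceptable rate 10%, unacceptable rate 25%, expected range 5-20%. From Section 2: the centre's own series, "Of 347 subjects, 10.1% experienced" at least one major complication. The number untreated, k, is not in the documents. It is assumed to be 1 to 5.

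**Step 1: the plan's own figures.** P(accept) = P(X ≤ 3), with X ~ Bin(25, p).
- p = 0.10: 0.0718 + 0.1994 + 0.2659 + 0.2265 = 0.7636, stated as 76%.
- p = 0.25: 0.0008 + 0.0063 + 0.0251 + 0.0641 = 0.0963 from rounded terms (0.0962 unrounded), stated as 10%.

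Both are reproduced with 25 subjects at the procedure's risk.

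**Step 2: no replacement, limit kept at 3.** With k untreated subjects whose events count at rate u,

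P(accept) = Σ_j Bin pmf(j; k, u) × Bin cdf(3 − j; 25 − k, p).

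Setting u = 0 covers untreated subjects kept as event-free. It gives the same figure as dropping them, because both reduce to cdf(3; 25 − k, p). A positive u applies if they have standard surgery and their complications count.

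Example for k = 1, p = 0.25, where cdf(3; 24) = 0.1150 and cdf(2; 24) = 0.0398:
- u = 0.101: 0.899 × 0.1150 + 0.101 × 0.0398 = 0.1074.
- u = 0.20: 0.80 × 0.1150 + 0.20 × 0.0398 = 0.1000.

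P(accept) at a true 25% rate:

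| Untreated | u = 0 or dropped | u = 5% | u = 10.1% | u = 20% |
|---|---|---|---|---|
| 0 | 9.6% | 9.6% | 9.6% | 9.6% |
| 1 | 11.5% | 11.1% | 10.7% | 10.0% |
| 2 | 13.7% | 12.8% | 12.0% | 10.4% |
| 3 | 16.2% | 14.8% | 13.3% | 10.8% |
| 5 | 22.5% | 19.3% | 16.4% | 11.6% |

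**Step 3: the 76%.** At a true 10% rate with u = 0 or dropping, acceptance rises to 78.6% for one untreated and 86.7% for five. With u = 10.1% it stays at 76.3% for one to five. It falls only if untreated subjects do worse than the 10% assumed for the procedure. For one at u = 20%, with cdf(3; 24) = 0.7857 and cdf(2; 24) = 0.5643 at p = 0.10: 0.80 × 0.7857 + 0.20 × 0.5643 = 0.7414. The 76% is therefore not the figure at issue.

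**Step 4: what has to happen for the larger figures.** Three to five untreated is 3/25 = 12% to 5/25 = 20%. Those subjects must not be replaced, although Section 3 allows more than 25 to enrol. They must then be handled in one of two ways:
- *Counted as event-free.* This fits poorly with Section 2, which says "the operation itself and indications are standard of care". An untreated enrollee would normally still have surgery, with its own complications.
- *Dropped with the limit held at 3.* Section 6 does not provide for this, since its limit is defined for 25 only.

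**The case for a change.** The strongest case for a change is that every sample-size statement says enrolled, and that permission to enrol more than 25 is not a duty to replace. In almost every no-replacement scenario above, the rule becomes more lenient towards a procedure with 25% morbidity. Enrolling beyond 25 also opens the opposite question, because no limit is given for a larger number. With 28 treated and the limit at 3, power would be 69.5% and acceptance at a 25% rate 5.5%. One or two sentences would settle all this at almost no cost.

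The textual point stands: no replacement rule or evaluable set is written down. The arithmetic stands too. What does not stand is the step from there to a fault in the rule. Section 6 sets its limit for exactly 25, and its sentence is about the resection procedure. An untreated subject is off protocol under Section 4. Over-enrolment to make up 25 treated leaves the rule as stated.

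Adding text is also less simple than it looks. A definition based on needle or marker placement would leave open the subject who is anaesthetised and scanned in the suite but never has a needle passed. That subject matters for the feasibility aim, and the line drawn would need its own justification.

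**Conclusion.** No change follows. The plan leaves out a detail that an analyst would fill sensibly by applying the rule to 25 subjects who had the procedure. On that reading both stated figures are exact to rounding (76.4% and 9.6%).

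If the detail were instead filled badly, only the false-acceptance figure would be at real risk. With one untreated subject it would be 10.0% to 11.5%, at most 1.9 points above 9.6%. With two it would be 10.4% to 13.7%, and with three 10.8% to 16.2%. The 22.5% for five is an upper bound. It needs 20% untreated, no replacement, and either event-free counting or a limit that Section 6 does not give.

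This conclusion rests on few subjects being lost between consent and surgery. The documents give no rate. They do say that subjects are already scheduled for resection and that the study radiologist and the surgeon review the CT before enrolment, so a large loss is not the natural expectation. If the number treated did differ from 25, the exact binomial figures for that number could be given in the report.
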